**Figure 1: Reader Study Work Flow**

## 7.2 Schedule of Reader Sessions

All reads will include standard reader training on an image viewing workstation, eCRF completion, etc.

Imagio (IUS +OA) training and a proficiency test will take place prior to the start of all study reads.

[figure not shown]
### 7.3 Description of Reading Environment

After completion of standard training and Imagio (IUS+OA) training, each of the readers will use an image display and electronic data capture workstation to perform image analysis, working alongside an ACR Read Monitor, for all reading sessions. Each reader and read monitor will be in a designated, private reading room for their use during a reading session. Readers will work undistracted so that their attention is focused on an accurate interpretation. The workstation desk will have adjustable height for reader comfort, the room will be equipped with noise abatement features, diagnostic display monitors and moderate illumination. As part of reader training and as documented in the confidentiality agreement they sign during the ACR CRI contracting process, readers will be aware and monitored to maintain confidentiality on study details and subject images reviewed. Access to the reading rooms is controlled and read monitors ensure readers do not take any unauthorized material into the reading rooms.

### 7.4 Graphical Interface for BI-RADS Category and POM Rating;

For the purpose of this study, the Readers will use a graphical interface to indicate their assessment of the BI-RADS category and POM rating for IUS and Imagio (IUS+OA) modalities (see *Figure 2*).

The POM scale is linear for all BI-RADS categories; however, the scale for BI-RADS 3 is expanded ten-fold compared to other categories. This design allows for a finer gradation of the malignancy rating for BI-RADS 3 lesions, which in turn provides more data points for the ROC curve and enables a better estimation of the partial AUC. One advantage of a graphical metaphor is that it provides an aid to the Reader in converting the BI-RADS feature lexicon to a numerical POM scale.

*Figure 2. Graphical input of BI-RADS category and POM rating.*

### 7.5 Randomization

BBRF will generate the randomized study read list.

### 7.6 Blinding

The readers will be blinded to the diagnosis, but the reader will have access to the following baseline variables:

- Age
- Indication (reason study was ordered)
- Mass location
- Medical History
- Mammograms (if available)

## 8. SAFETY ASSESSMENTS

Safety assessments are not required as this is a reader study of de-identified Imagio (IUS+OA) and IUS images. No patient diagnoses are affected by the reader sets or this MRM study.

## 9. STATISTICAL CONSIDERATIONS

### 9.1 General Design Issues

BBRF will implement the Feasibility Study sampling plan to represent the PIONEER Pivotal Study masses to reflect mammography use and site CDU BI-RADS score.

BBRF will determine which masses are to be assigned to each cohort; Cohorts 1-3 will be the same across all readers.

The unit of measurement for reader-based outcomes is at the reader-mass level. The Feasibility Study will be used to assess if independent readers can conduct pre-specified POM evaluations separately for IUS and then for Imagio (IUS+OA) and the Senogram to evaluate the primary and secondary effectiveness endpoints. Pre-specified POM evaluations will be performed separately for IUS, Imagio (IUS+OA), and the reader use of the SenoGram to evaluate the Imagio (IUS+OA) and SenoGram specificities and sensitivities.

The primary endpoint is to show a specificity advantage for fixed sensitivity; this diffuses the tradeoff between FNs and FPs if the FN rate is the same. These sensitivity and specificities will be calculated overall and per reader using generalized estimating equations (GEE) and the analysis of variance (ANOVA) modeling as well as for observed without adjustment.

For each endpoint, Imagio will be compared versus IUS; the same analyses will be performed for the SenoGram versus IUS and Imagio.

The specificity advantages will be computed for fixed sensitivity (e.g. 98% target) with interpolation or extrapolation used by calculating the specificities and sensitivities from the ROC curve as needed. This same principle will be used to construct the partial ROC curves and to compute the area under the ROC curve to correspond to 95-99% sensitivity.

The results from the Feasibility Study will be used to judge if there is sufficient rationale to proceed to a pivotal study involving more masses and more readers to support the indications for use. If there is sufficient strength of the data, then the Imagio Feasibility Study results will be used to determine the pivotal study sample size. The effect sizes will be assessed to judge if the pivotal study can be conducted with at least 80% power for two-sided hypothesis testing with 5% Type I error; this depends on the effect sizes achieved for the primary and secondary effectiveness endpoints as well as inter-reader variabilities.

Feasibility Study data will not be used or combined with any subsequent pivotal study data, but the same masses used in the Feasibility Study may be used in the subsequent pivotal study.

The Feasibility Study will not test any formal statistical hypotheses but will be used to formulate hypotheses to be formally tested in the pivotal study.

A move forward decision will be made based on the collective performance of the primary and secondary effectiveness endpoints using Cohort 1 (75 benign masses and 45 malignant masses). Cohort 2 will give separate confidence that training has helped to reduce FNs. Cohorts 1, 2 and 3 will be analyzed separately.

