### 4. STUDY DESIGN

This will be a single arm, controlled, blinded, multi-reader, multi-case (MRMC) study using a sequential design. The study will include 5-12 readers depending on qualifications and availability.

Imagio (IUS+OA) Training to be completed prior to any reads taking place. Read 1 is immediately followed by Read 2 within the same read session.

- Read 1 (Control): Mammogram (if available) + History + IUS (stills and videos provided), IUS Probability of Malignancy (POM) and BI-RADS scored and the data form locked.
- Read 2 (Test): Mammogram (if available) + History + IUS (stills and videos provided), and Imagio (IUS+OA) (stills and videos provided). An interim IUS POM and BI-RADS is recorded as well as a combined Imagio (IUS+OA) POM and BI-RADS Pre and Post SenoGram on separate data forms.

Read 1 reflects the information available to a radiologist when evaluating standard ultrasound images, taking under consideration the mass and patient history and assessing mammogram results as available. The History details to be provided are summarized under the Blinding section of the protocol. Read 1 (IUS reads) will serve as the control representing current clinical practice. Read 2 (IUS+OA) will be considered the test read and reflect a pre SenoGram IUS and Imagio (IUS+OA) POM and BI-RADS assessment in addition to a post SenoGram IUS and Imagio (IUS +OA) POM and BI-RADS assessment. Following the display of the SenoGram within the Post SenoGram data form, the IUS and OA feature scores are locked, and the reader is prompted to provide a Post SenoGram POM and BI-RADS. Once the Post SenoGram POM and BI-RADS are provided, the form is locked.

A total of 155 complete read sets from the original PIONEER Intention-to Diagnose (ITD) population will be randomly selected from within the PIONEER Study.

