- Comprising the 155 mass read sets, the first cohort will consist of 75 benign and 45 malignant masses (reflecting the same 37.5% prevalence of cancer as for the overall pivotal ITD population), classified by conventional diagnostic ultrasound (CDU) as BI-RADS 3 to 5 to be selected at random in proportion to the original assignment distribution of BI-RADS classifications among subjects in the PIONEER Study. To facilitate the alignment of the PIONEER Pivotal Study data with the Feasibility Study data, the mass image set sampling plan will select a proportion with and without mammograms depending on availability of the mammograms, separately for benign and malignant masses. Cohort 1 will be used for the effectiveness endpoint analyses in support of decision making. The same sampling strategy will be used to ensure a comparable proportion of mass image sets as for the PIONEER Pivotal Study.

- The second cohort consists of 30 additional malignant masses for which 1 or more pivotal study readers scored the mass a false negative during a read from the PIONEER study; this will assess if the excess FN rate observed with OA in the PIONEER study can be reversed.
- The third cohort will consist of five DCIS, lymphoma, or Phyllodes masses; this will assess how these atypical cases will be scored. Since there are so few of these cases, mammogram matching will not be possible.

This evaluation will further achieve the following:

1. The incremental contributions of IUS and Imagio (IUS+OA) by assessing the BI-RADS and POM values at each step in the read order traditionally used in clinical practice.
2. The SenoGram performance versus IUS and versus Imagio (IUS+OA) once IUS + OA features are scored with subset evaluation of the effect of presence or absence of the mammographic data on Senogram performance.

The SenoGram is a classification model that predicts the probability that a lesion is malignant for a given set of reader-assigned feature scores and other relevant data. For this study, the SenoGram will consist of two components, a user interface and a back-end computation engine. The reader will enter feature data into the user interface. When all data has been entered, but prior to a final submission of the data, the user interface will graphically display the model's predicted likelihood of malignancy [not to be confused with POM].

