1.1. Statistical and Analytical Plans

1.1.1. Definitions and General Considerations for Data Analysis

1. All calculations will be performed in a GCP-compliant environment using SAS statistical software, version 9.2 or later, StatXact, version 10 or later or OR-DBM MRMC (2.5) or later.
2. This Statistical Analysis Plan (SAP) is based on Clinical Trial Protocol Imagio Feasibility MRMC Study of Optoacoustic Images vs. Imagio Ultrasound to Guide Decision to Biopsy, September 24/November 1, 2018 – Version 3.0.
3. This study is a single arm, controlled, blinded, multi-reader, multi-case (MRMC) study using a sequential design.
4. This feasibility study will be registered at clinicaltrials.gov.
5. There will be up to 12 independent readers to evaluate images using standardized equipment at American College of Radiology (ACR).
6. All readers will read all images utilizing (IUS) and before (IUS+OA pre) and after the SenoGram (SG) prompt (IUS+OA post); prior to all image reads, all readers will have access to mammography images and a clinical history as collected in PIONEER.
7. A total of 155 complete read sets from the original PIONEER Intention-to-Diagnose (ITD) population will be randomly selected from within the PIONEER Study. Only once mass is to be selected per PIONEER subject.
 - Cohort 1 will consist of 75 benign and 45 malignant masses classified by CDU as BI-RADS 3 to 5 selected at random in proportion to the original distribution of Bi-RADS classifications among subjects in the PIONEER Study. To facilitate the alignment of the PIONEER Pivotal Study data with the Feasibility Study data, the mass image set sampling plan will select a proportion with and without mammograms for benign masses. [Note: mammograms were present for nearly all malignant masses.]
 - Cohort 2 will consist of 30 malignant masses with at least one false negative read from the PIONEER study to assess if the excess FN rate observed with OA in the PIONEER study can be reversed. The same proportional sampling strategy with respect to CDU Bi-RADS will be used. Cohort 3 will consist of five DCIS, lymphoma, or phyllodes masses; this will assess if these atypical cases do not introduce FNs or FPs. [Note: Due to the small size, Cohort 3 results will be listed only and not be summarized.]
8. Cohort data will not be combined across cohorts.

9. To assess intermediate performance an interim analysis is planned after each reader has completed at least 72 Cohort 1 masses.

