
b) Specificity at fixed sensitivity (98%) for SenoGram classification as in (a).
 
c) Partial AUC (over sensitivity range 95% to 99%, inclusive, using the McClish normalization) for SenoGram classification as in (a).
 
d) Partial AUC (over sensitivity range 95% to 99%, inclusive, using the McClish normalization) for SenoGram classification as in (a).
 
e) Sensitivity and specificity for SenoGram classification based on prediction intervals and the SenoGram threshold. The prediction will be considered inconclusive if the SenoGram threshold lies within the prediction interval; otherwise the interval prediction is treated the same as a probability prediction. As in (a), each cohort will be analyzed separately, with subgroup analysis for masses with and without mammogram BI-RADS data.
 
f) Specificity at fixed sensitivity (98%) for SenoGram classification using the prediction interval as in (d).
 
Partial AUC (over sensitivity range 95% to 99%, inclusive, using the McClish normalization) for SenoGram classification using the prediction interval as in (d).
	
PIONEER data.

Cohort 1: Exploratory
	

OA Feature Score Distributions:
 
 • Benign vs. malignant masses • Benign masses only – mammogram vs no mammogram 
POM Score Distributions:
	
Summary Statistics by reader. Average over readers and then summarize means for overall. Use Wilcoxon for test statistic.
 
Reference PIONEER T14.2.10.1 [t_14_02_1x_feat-10-_01]

 Benign vs. malignant masses Benign masses only – mammogram vs no mammogram 	Reference PIONEER Table 14.2.9.1 [t_14_02_09_pom-01]
Cohort 2: Secondary	
Observed and model-adjusted sensitivity	SAS: PROC GEE and MIXED
BI-RADS: Up and downgrades (defined above) for cancers only	
SAS: BI-RADS Grade Changes (Grouped BI-RADS), simple counts with two-sided 95% CI.
 
Cancers: Reference PIONEER Table 14.2.13.7 [t_14_02_13_birch2_07]
 
Note: change from 99% CI to 95% CI
 
Tables to be repeated for IUS x IUS+OA post, IUS vs IUS+OA pre and IUS+OA pre vs IUS+OA post

Cohort 3: Listings Only	

All Cohorts (Combined)
 
Summary statistics to describe the SenoGram usage [n(%)] by individual reader and overall. Summary statistics for the SenoGram effect on reader confidence.
	SAS: Proc Freq & Proc univariate

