1.1.7.1. Feasibility Analysis Methodology

Data Analyses

Hypotheses generating analyses will be based on independent readers for POM, BI-RADS and feature scores (IUS, IUS+OA pre, IUS+OA post) individually and overall. There are no formal hypothesis tests; p-values from all analyses are descriptive only. There are no adjustments for multiple testing. There will be no adjustment in p-values reported for the planned interim analysis after a minimum of 72 reads by each reader in Cohort 1. Truth (determination of malignant biopsy, benign biopsy, or TPB) will be taken from PIONEER.

The analyses below will be done for Cohort 1, repeated for malignant masses only for cohort 2. No summaries (listings only) will be done for the 5 masses in Cohort 3.

The specificity advantage of IUS+OA post vs IUS, IUS+OA pre vs IUS and IUS+OA post vs IUS+OA pre will be compared at fixed 98% sensitivity. The software package OR-DBM MRMC [Version 2.5 or later] will be used for this analysis of OA gain as interpolated from the ROC curves.

Specificity and sensitivity will be calculated by reader and overall for IUS, IUS+OA pre, IUS+OA post, and the 3 pairwise differences [PROC GENMOD, readers as independent,

repeated as masses as independent]. Specificity and sensitivity will be calculated (not model-adjusted) using the 2% POM cutoff for IUS+OA pre, IUS+OA post and IUS; and then for robustness analyses, for 1%, 3%, 4%, and 5% cutoffs.

Clinically relevant up and downgrades based on BI-RADs are defined as:

- Downgrades: IUS in BR 4a and IUS+OA post in BR 2-3 or IUS in BR 3 and IUS+OA post in BR 2
- Upgrades: IUS in BR 2 and IUS+OA post in BR 3-5 or IUS in BR 3 and IUS+OA post in BR 4-5.

These definitions likewise hold for differences for IUS vs IUS+OA pre and IUS+OA pre and IUS+OA post. These clinically relevant up and downgrades will be reported by reader and overall for benign and cancers separately. For benign masses, up and downgrades will be reported for masses with and without mammograms.

To assess the net effect of downgrades and upgrades, a net gain will be computed in SAS using contrast statements for the ANOVA to determine weight (W) of the malignant outcomes (TP and FN) to determine the value $(A-B+W(C-D))$ that achieves statistical significance, where A, B, C and D are defined as:

- A. Benign Masses correctly downgraded using IUS+OA post
- B. Benign Masses incorrectly upgraded using IUS+OA post
- C. Malignant masses correctly upgraded using IUS+OA post

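### Cohort 2 cannot show that training reduced false negatives: every read follows training, and its masses were selected on a PIONEER false negative

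*Protocol*

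**What the plan says.** Protocol 9.1 (General Design Issues) assigns the move-forward decision to Cohort 1 and then states that "Cohort 2 will give separate confidence that training has helped to reduce FNs".

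Cohort 2 is 30 malignant masses. Protocol section 4 takes those for which "1 or more pivotal study readers scored the mass a false negative during a read from the PIONEER study". SAP 1.1.1 item 7 has the same rule: "Cohort 2 will consist of 30 malignant masses with at least one false negative read from the PIONEER study". It adds: "The same proportional sampling strategy with respect to CDU Bi-RADS will be used". Neither passage says whether the qualifying FN was an ultrasound (IUS) read or an opto-acoustic (OA) read. Both give the aim as seeing whether the OA excess of FNs found in PIONEER can be reversed.

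On timing, Protocol section 4 has "Training to be completed prior to any reads taking place", and Protocol 7.2 says that "training and a proficiency test will take place prior to the start of all study reads".

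For Cohort 2 readers, SAP Table 1 (section 1.1.7) lists "Observed and model-adjusted sensitivity" and BI-RADS grade changes in cancers. SAP 1.1.7.1 adds: "The analyses below will be done for Cohort 1, repeated for malignant masses only for cohort 2". Those analyses include probability-of-malignancy summaries with pairwise differences and feature scores. The reader comparisons are among IUS, IUS+OA before the SenoGram and IUS+OA after it.

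**The concern.** To say that FNs were reduced needs a reference, and to credit training needs a contrast between trained and untrained reading. The study has no untrained reads. The reference left is PIONEER, and the Cohort 2 masses were picked because a PIONEER read failed on them.

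Part of what made those reads fail is read-to-read chance. A new set of reads does not carry that chance over, so the FN rate on these masses should fall with nothing changed. This is regression to the mean after selection on the outcome. Sampling in proportion to the site BI-RADS category does not undo it, because the selection is on the FN itself.

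At stake is the sponsor's belief, carried into the pivotal study, that the training programme works. Read as written, the sentence turns an expected artefact into support for training.

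**Working it through.** **1. Does any planned contrast isolate training?** The Cohort 2 reader outputs are sensitivity, grade changes, probability-of-malignancy summaries and feature scores for IUS, IUS+OA pre and IUS+OA post. The same trained readers supply all three. Pre versus post isolates the SenoGram display, and IUS versus IUS+OA isolates the added images. None isolates training. The SenoGram performance row of SAP Table 1 does set cohort results beside predictions from PIONEER data, but that concerns the model, not reader FNs.

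**2. What should re-reading show with no training effect?** The documents give no FN rate, expected reduction or power for Cohort 2, so there is no figure to reproduce. All inputs below are assumed.

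- m: mean FN probability over cancers
- rho: within-mass correlation of reads
- R: PIONEER reads per cancer in the selecting modality
- p: a mass's own FN probability, Beta(a, b) with mean m and a+b = 1/rho − 1

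A mass is kept if at least one of R reads is an FN.

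- P0 = E[(1−p)^R] = product over i = 0..R−1 of (b+i)/(a+b+i)
- PIONEER FN rate on kept masses = m/(1−P0)
- Expected FN rate on re-reading = (m − E[p(1−p)^R])/(1−P0)
- Relative fall = E[p(1−p)^R]/m = product over i = 0..R−1 of (b+i)/(a+b+1+i)

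The fall is above 0 unless p is always 0 or 1, that is, unless reads of a mass never vary.

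**3. One case in full.** m = 0.05, rho = 0.2, R = 7, so a+b = 4, a = 0.2, b = 3.8.

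- P0 = 0.950 × 0.960 × 0.967 × 0.971 × 0.975 × 0.978 × 0.980 = 0.800
- PIONEER rate = 0.05/(1 − 0.8001) = 25.0%
- Relative fall = 0.760 × 0.800 × 0.829 × 0.850 × 0.867 × 0.880 × 0.891 = 0.291
- Re-read rate = 25.0% × (1 − 0.291) = 17.7%

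**4. Other numbers of reads, same m and rho.**

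| R | PIONEER, same masses | Re-read, no training effect | Relative fall |
|---|---|---|---|
| 2 | 56.8% | 22.3% | 61% |
| 5 | 30.3% | 19.1% | 37% |
| 7 | 25.0% | 17.7% | 29% |
| 10 | 20.9% | 16.3% | 22% |
| 12 | 19.2% | 15.7% | 18% |

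**5. Range.** With m from 2% to 10% and rho from 0.1 to 0.6, the relative fall is 5% to 59% for R of 5 to 10. For R of 2 to 12 it is 4% to 79%, or 1.8 to 41.8 percentage points. The ends are m = 10%, rho = 0.6, R = 12 and m = 2%, rho = 0.1, R = 2.

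**6. How often would one study of 30 masses look improved?** Simulation with m = 5%, R = 7, 5 to 12 new readers and no training effect: at rho = 0.3 the new rate was below PIONEER's on the same masses in 94% to 97% of studies. Over rho from 0.5 to 0.1 the span was 86% to more than 99.9%.

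**7. Two conditions on the direction.**

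- *Same masses.* In step 3 the re-read rate of 17.7% is far above the assumed overall rate of 5%. In the step 5 grid it is at least 1.4 times the overall rate in every cell. Against PIONEER's overall rate, Cohort 2 should look worse.
- *Same modality.* Suppose selection used IUS FNs only and errors are independent given the mass. With the step 3 inputs, the OA FN rate on the selected masses is then 17.7% in PIONEER and 17.7% on re-reading: no fall.

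**The case against.** The strongest reply is that no document specifies a comparison of Cohort 2 reader FNs with PIONEER. The stated aim is reversal of the OA excess, and the sentence in Protocol 9.1 can be read in that light; the planned IUS versus IUS+OA contrasts bear on it. The first part stands: the objection is to an interpretation written in the protocol, not to a planned test. The second does not rescue the sentence, because it names training as the cause and no contrast between trained reads can show that.

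A second reply is that the size is uninformative, since every input is assumed and the range is wide. That is right, and no single figure should be quoted as the bias. The argument needs only the direction.

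A third is that little depends on it. Protocol 9.1 bases the move-forward decision on Cohort 1 and analyses the cohorts separately, Protocol 9.8 makes p-values descriptive, and the SAP does not repeat the claim about training. This stands and limits the weight of the point.

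A reader might infer more: that the move-forward decision is biased, that Cohort 2 fails its stated aim on the OA excess, or that a fall from PIONEER is certain on any comparison. The documents do not support these. The decision rests on Cohort 1; the point here does not address the OA excess; and the direction depends on the two conditions in step 7, with the selecting modality not named.

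**Conclusion.** The sentence in Protocol 9.1 is wrong as written. That Cohort 2 cannot isolate training follows from the design alone, without any model. That a lower FN rate than PIONEER recorded is expected from selection holds for the same masses, in the selecting modality, whenever reads of a mass vary. The size cannot be fixed from the documents; about 4% to 79% relative is a range over assumed FN rates, correlations and numbers of PIONEER reads. It is a low-impact point with a cheap remedy in an unpowered feasibility study.

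**What to change.** Replace the sentence in Protocol 9.1 with: *Cohort 2 results are descriptive and do not isolate a training effect. Because these masses were selected on a PIONEER FN, a lower FN rate than PIONEER recorded on the same masses is expected from selection alone.*

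No SAP analysis needs to be added. If a comparison with PIONEER reader FNs is reported all the same:

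- Compare with a selection-corrected PIONEER rate from existing reads, not the raw rate on the selected masses. One way is to leave out one reader at a time: select on the others and score the one left out. With the step 3 inputs this gives 18.3%, slightly above the 17.7% target but far nearer than the raw 25.0%.
- Use the same FN definition and the same modality in both studies.
- Attribute any further fall to the whole reading process, not to training alone. The readers, the SenoGram and the graphical rating interface all form part of that process.

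The cost is one sentence and, only if the comparison is made, one analysis of existing reads. The downside is that the apparent FN reduction becomes smaller, and the corrected comparison still does not isolate training.
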